## CLINICAL TRIAL PROTOCOL SYNOPSIS

Name of company:		Boehringer Ingelheim	
Name of finished product: Ofev®			
Name of active ingredient: Nintedanib			
Protocol date: 11 Feb 2016	Trial number: 1199.227	Revision date: 09 Jul 2018	
Title of trial:	A 12-week, double blind, randomised, placebo controlled, parallel group trial followed by a single active arm phase of 40 weeks evaluating the effect of oral nintedanib 150 mg twice daily on change in biomarkers of extracellular matrix (ECM) turnover in patients with idiopathic pulmonary fibrosis (IPF) and limited forced vital capacity (FVC) impairment.		
Coordinating Investigator:			
Trial site(s):	Multi-centre, multi-national trial		
Clinical phase:	IV		
Objective(s):	To investigate the effect of nintedanib on various extracellular matrix (ECM) turnover biomarkers and the predictive value of change in those ECM biomarkers on disease progression.		
Methodology:	12-week randomised, double blind, parallel group, placebo controlled phase followed by a single active arm phase of 40 weeks		
No. of patients:	~490 enrolled (screened) patients		
total entered:	~350 entered (randomised) patients		
each treatment:	Nintedanib: 117 Placebo: 233 * *applicable to 12-week randomised part of the trial		
Diagnosis :	Idiopathic Pulmonary Fibrosis (IPF)		
Main criteria for inclusion:	Male or female patients aged ≥40 years at Visit 1 (screening); IPF diagnosis based upon ATS/ERS/JRS/ALAT 2011 guideline within 3 years of Visit 0; HRCT		

Name of company:		Boehringer Ingelheim	
Name of finished product: Ofev®			
Name of active ingredient: Nintedanib			
Protocol date: 11 Feb 2016	Trial number: 1199.227		Revision date: 09 Jul 2018
	performed within 18 months of Visit 0; confirmation of diagnosis by central review of chest HRCT and surgical lung biopsy (later if available) prior to randomisation; FVC ≥ 80% predicted of normal at Visit 1 (screening)		
Test product(s):	Nintedanib		
dose:	300 mg daily (150 mg bid) with possibility to reduce total daily dose to 200 mg (100 mg bid) to manage adverse events (AEs)		
mode of administration:	oral		
Comparator products:	Placebo matching Nintedanib		
dose:	Not applicable		
mode of administration:	oral		
Duration of treatment:	52 weeks		
Endpoints	
Primary Endpoint:
 
 
Rate of change (slope) in blood CRPM from baseline to week 12
 
 
Key Secondary Endpoint:
 
 
Proportion of patients with disease progression as defined by absolute FVC (% predicted) decline ≥10% or death until week 52
 
 
Secondary Endpoints:
 
 
Rate of change (slope) in blood C1M from baseline to week 12
 
Rate of change (slope) in blood C3M from baseline to week 12
 
 
Further Endpoints (selected):
		

Name of company:		Boehringer Ingelheim	
Name of finished product: Ofev®			
Name of active ingredient: Nintedanib			
Protocol date: 11 Feb 2016	Trial number: 1199.227		Revision date: 09 Jul 2018
Safety criteria:	Adverse events (especially SAE and other significant AE), physical examination, weight measurements, 12 lead electrocardiogram, vital signs and laboratory evaluations.		
Statistical methods:	Random coefficient regression models for continuous endpoints, Log rank tests, Kaplan-Meier plots and Cox regressions for time to event endpoints, logistic regression models or other appropriate methods for binary endpoints		

11. To be performed **after** pre-dose PK sample (if applicable) and **after** current visit exams.
12. Perform only if abnormal or findings needing follow-up recorded at Visit 10.
13. Visit 1 should only be conducted after IPF diagnosis has been confirmed by central review.
14. In case of dose change of nintedanib (reduction or re-escalation), dose adjustment visit must be conducted to allow dispensing of new medication kit.
15. Early end of treatment visit to be completed for all patients who withdraw or discontinue study treatment prematurely. Patients who prematurely discontinue treatment will then be invited to attend all visits as planned until week 52 (Visit 10).
16. Screening period (period between Visit 1 and 2) should last 14 days (2 weeks). The screening period may be prolonged by additional 2 week for any reasons, i.e. total 28 days (4 weeks). Eligible patients can be randomised once central lab results have been received and are found to be consistent with eligibility criteria.
17. 4 days prior to planned PK sampling site should preferably contact the patient to record times of drug intake within patient diary. Patient should record times of drug intake three days prior to the PK sampling.
18. In women of childbearing potential.
19. Applicable only if patient doesn't accept to attend remaining scheduled visits.

## ABBREVIATIONS

AE	Adverse Event
AESI	Adverse Event of Special Interest
ALAT	Latin American Thoracic Association
ALP	Alkaline phosphatase
ALT	Alanine transaminase
AST	Aspartate aminotransferase
ATP	Adenosine triphosphate
ATS	American Thoracic Society
AUC	Area under the Curve
b.i.d.	bis in die (twice daily dosing)
BI	Boehringer Ingelheim
BIRDS	Boehringer Ingelheim Regulatory Documents for Submission
BS	Biomarker Set
C1M	Collagen 1 degraded by MMP-2/9/13
C3M	Collagen 3 degraded by MMP-9
CA	Competent Authority
CI	Confidence Interval
CML	Local Clinical Monitor
CNS	Central Nervous System
CRA	Clinical Research Associate
CRF	Case Report Form
CRO	Clinical Research Organisation
CRPM	C-reactive protein degraded by MMP-1/8
CTCAE	Common Terminology Criteria for Adverse Events
CTP	Clinical Trial Protocol
CTR	Clinical Trial Report
DDI	Drug-drug interaction
DEDP	Drug exposure during pregnancy
DILI	Drug induced liver injury
DLCO	Carbon monoxide diffusing capacity
DMC	Data Monitoring Committee
DNA	Deoxyribonucleic Acid
eCRF	Electronic Case Report Form
ePRO	Electronic Patient Reported Outcome
ECG	Electrocardiogram
ECM	Extracellular matrix
EDC	Electronic Data Capture
EDTA	Ethylendiamintetraacetate
EOT	End of treatment

ERS	European Respiratory Society
EudraCT	European Clinical Trials Database
FAS	Full Analysis Set
FC	Flow Chart
FDA	Food and Drug Administration
FGFR	Fibroblast growth factor/receptor
FVC	Forced vital capacity
GCP	Good Clinical Practice
GGT	Gamma-glutamyl transferase
GI	Gastrointestinal
β-HCG	β-human Chorionic Gonadotropin
HPC	Human Pharmacology Center
HRCT	High Resolution Computer Tomography
IB	Investigator's Brochure
ICH GCP	International Conference on Harmonisation Good Clinical Practice
IEC	Independent Ethics Committee
INR	International normalised ratio
IPF	Idiopathic pulmonary fibrosis
IRB	Institutional Review Board
IRT	Interactive Response Technology
ISF	Investigator Site File
i.v.	intravenous
IVRS	Interactive Voice Response System
IWRS	Interactive Web-based Response System
JRS	Japanese Respiratory Society
LC-MS/MS	Liquid chromatography-tandem mass spectrometry
LDH	Lactate dehydrogenase
LoEE	List of Essential Element
MedDRA	Medical Dictionary for Drug Regulatory Activities
MMPs	Metalloproteinases
MMRM	Mixed Effects Model for Repeated Measures
MST	Medical Sub team
N/A	Not Applicable
NAC	n-acetylcysteine
nRTKs	Non-receptor tyrosine kinases
OPU	Operative Unit
p.o.	per os (oral)
PCC	Protocol Challenge Committee
PD	Pharmacodynamic/ Pharmacodynamics
PDGFR	Platelet derived growth factor/receptor

PFT	Pulmonary Function Test
PG	Pharmacogenetics
PK	Pharmacokinetic Set
PKS	Pharmacokinetic/ Pharmacokinetics
PT	Prothrombin time
PTT	Partial thromboplastin time
q.d.	quaque die (once a day)
RDC	Remote Data Capture
REP	Residual effect period, after the last dose of medication with measurable drug levels or pharmacodynamic effects still likely to be present
RS	Randomised Set
RTKs	Receptor tyrosine kinases
SAE	Serious Adverse Event
s.c.	Subcutaneous
SGRQ	St. George's Respiratory Questionnaire
SOP	Standard Operating Procedure
SPC	Summary of Product Characteristics
SP-D	Surfactant Associated Protein-D
SpO2	Oxygen Saturation
TCM	Trial Clinical Monitor
TDMAP	Trial Data Management and Analysis Plan
t.i.d.	ter in die (3 times a day)
TMF	Trial Master File
TMW	Trial Medical Writer
TS	Treated Set
TSAP	Trial Statistical Analysis Plan
TSH	Thyroid stimulating hormone
UIP	Usual Interstitial Pneumonia
ULN	Upper Limit Normal
UCSD-SOBQ	UCSD Shortness of Breath Questionnaire
VEGFR	Vascular endothelial growth factor/receptor

## 1. INTRODUCTION

### 1.1 MEDICAL BACKGROUND

Idiopathic pulmonary fibrosis (IPF) is a rare disease of unknown aetiology that is characterized by progressive fibrosis of the interstitium of the lung, leading to decreasing lung volume and progressive pulmonary insufficiency [[P11-07084](#)].

The course of the disease in individual patients is variable: some patients progress rapidly, others have periods of relative stability punctuated by acute exacerbations and others progress relatively slowly. Acute exacerbations of IPF are events of respiratory deterioration of unidentified cause that occur in 5–10% of patients annually and are associated with a very poor outcome [[R12-2786](#)].

IPF is most prevalent in middle aged and elderly patients, and usually presents between the ages of 40 and 70 years. The median life expectancy in IPF patients after diagnosis is 2 to 3 years [[P11-07084](#)].

The latest update on clinical practice guideline for the treatment of IPF, jointly issued in 2015 by the American Thoracic Society (ATS), European Respiratory Society (ERS), Japanese Respiratory Society (JRS) and Latin American Thoracic Association (ALAT) has provided a conditional recommendation for treatment with nintedanib or pirfenidone for the majority of IPF patients, taking into account individual patient values and preferences [[P15-07362](#)]. Conventional IPF treatments such as n-acetylcysteine (NAC), corticosteroids, cyclophosphamide, cyclosporine and azathioprine are not approved treatments for IPF, and their efficacy is questionable or even harmful [[P15-07362](#); [P12-06085](#); [P14-07665](#)]. Non-pharmacological therapies such as pulmonary rehabilitation and long-term oxygen therapy are recommended for some patients, but their efficacy in patients with IPF has not been established. Lung transplant has been shown to positively impact survival in patients with IPF. [[R11-5086](#); [R12-2785](#)]. Although the number of patients transplanted due to IPF has increased steadily over the last years, the scarce availability of donor organs, as well as the comorbidities and advanced age preclude many patients from referral to lung transplant [[R12-3676](#); [R12-3474](#)].

Pirfenidone, a compound which demonstrated anti-fibrotic activity in non-clinical models, was first licensed in Japan in 2008 based on two local trials which showed a reduced decline of vital capacity under treatment with the compound [[R06-2070](#); [R10-4316](#)]. In the international Phase III CAPACITY program, pirfenidone demonstrated efficacy on the primary FVC lung function endpoint in only one of two confirmatory trials [[R11-4827](#)]. The additional confirmatory ASCEND Phase III trial requested by FDA met the primary endpoint of change from baseline FVC % predicted [[R14-2103](#)]. Pirfenidone is also licensed since February 2011 for the treatment of mild to moderate IPF in the European Union and since October 2014 for the treatment of IPF in the United States of America. It is also licensed in several other countries.

Nintedanib is a small molecule intracellular tyrosine kinase inhibitor which has demonstrated anti-fibrotic and anti-inflammatory activity in preclinical models [[P08-08684](#); [P14-02860](#)]. The two replicate Phase III INPULSIS trials and the Phase II TOMORROW trial consistently showed positive results for the efficacy of nintedanib 150 mg twice daily versus placebo in

patients with IPF. Both INPULSIS trials showed that nintedanib reduced the annual rate of decline in FVC (mL/year) by approximately 50%, consistent with slowing disease progression [[P14-07514](#); [P11-11216](#)]. Based on these three clinical trials, nintedanib was approved for the treatment of IPF in the USA in October 2014, in the European Union in January 2015 and in Japan in July 2015. As of 20 October 2015, nintedanib has also been approved in Canada, Switzerland, Russia, Australia, Chile, Ecuador and Taiwan and it has been submitted for marketing authorization in other countries across the world.

Although nintedanib and pirfenidone can be considered a standard of care for patients diagnosed with IPF, it remains unclear when to start and when to stop treatment with either of the drugs, given the unpredictability of clinical course in the individual patient as well as the lack of biomarkers to inform patient management and therapeutic response.

With the introduction of nintedanib in the treatment algorithm of IPF, there is an additional need to further characterize its profile in patients at an early disease stage, i.e. in patients with limited lung volume impairment, and to address the question when to start treatment in these patients. Currently, many physicians apply a wait and watch strategy for these patients as there are no markers to predict the individual course in a given patient or response to treatment which may result in a delay of treatment initiation. Identifying biomarkers to predict the clinical course and benefits of therapy for a given patient early in the course of the disease remains one of the most urgent and relevant challenges in patient management

## 1.2 DRUG PROFILE

Nintedanib is a small molecule that inhibits a distinct spectrum of receptor tyrosine kinases (RTKs) and non-receptor tyrosine kinases (nRTKs) at pharmacologically relevant concentrations. Among them, FGFR (fibroblast growth factor/receptor), PDGFR (platelet derived growth factor/receptor) and VEGFR (vascular endothelial growth factor/receptor) have been implicated in IPF pathogenesis. Nintedanib binds competitively to the adenosine triphosphate (ATP) binding pocket of these receptors and blocks the intracellular signalling which is crucial for the proliferation, migration, and transformation of fibroblasts representing essential mechanisms of the IPF pathology [[P08-08684](#); [P14-02860](#)].

A soft gelatin capsule formulation of nintedanib is used in humans. Maximum plasma concentrations occur between 2 - 4 hours after oral administration. Steady state is reached at the latest within one week of dosing. After food intake, a trend towards an increased systemic exposure (around 15 to 20%) and a delayed absorption was observed compared to administration under fasted conditions. Nintedanib is recommended to be taken with food. Nintedanib is preferentially distributed in plasma, with a blood to plasma ratio of 0.87; the terminal half-life is in the range of 7 to 19 h. The absolute bioavailability of nintedanib was slightly below 5%. Nintedanib is mainly eliminated via faeces.

Co-administration of nintedanib with the P-glycoprotein (P-gp) inhibitor ketoconazole increased exposure to nintedanib by 60-70% based on area under the curve (AUC) and by 80% based on a maximum measured concentration of the analyte in plasma (Cmax) in a dedicated drug-drug interaction (DDI) study. Patients taking potent P-gp inhibitors (e.g ketoconazole, erythromycin or cyclosporine) should be monitored closely for tolerability of nintedanib.

In a DDI study with the P-gp inducer rifampicin, exposure to nintedanib decreased to 50.3% based on AUC and to 60.3% based on Cmax upon co-administration compared to administration of nintedanib alone. Since potent P-gp inducers may decrease exposure to nintedanib, selection of alternative treatment with no or minimal P-gp induction should be considered.

The clinical efficacy of nintedanib has been studied in over 1400 patients with IPF in one phase II dose finding study (TOMORROW) including four different doses of nintedanib, and two replicate phase III (INPULSIS 1 and 2) trials. These were randomised, double-blind, placebo-controlled studies comparing treatment with nintedanib twice daily to placebo for 52 weeks. A statistically significant reduction in the annual rate of decline of FVC (in mL) was demonstrated in patients receiving nintedanib 150 mg bid compared to patients receiving placebo. The treatment effect on FVC was consistent in all 3 studies, i.e. a relative reduction of approximately 50% between nintedanib and placebo. Furthermore, nintedanib 150 mg bid significantly reduced the risk of first acute exacerbation compared with placebo in INPULSIS-2 and in the TOMORROW trial, and reduced the risk of adjudicated confirmed/suspected acute exacerbations by 68% in a pre-specified sensitivity analysis of pooled data from the INPULSIS® trials, supporting the effect of nintedanib on slowing disease progression [[P14-07514](#); [P11-11216](#)].

The safety profile of nintedanib has been investigated comprehensively. The proportion of patients with serious adverse events was similar in the nintedanib and placebo groups.

The risks of treatment with nintedanib in adult patients are primarily related to the gastrointestinal tract (nausea, vomiting, diarrhea, abdominal pain) and to increases in liver enzymes aspartate aminotransferase (AST), alanine transaminase (ALT), alkaline phosphatase (ALP), gamma-glutamyl transferase (GGT) and bilirubin. The most frequently reported adverse event was diarrhea which was mild to moderate in intensity for the vast majority of patients and lead to treatment discontinuation in less than five percent of patients treated with nintedanib. Weight decrease and decreased appetite have also frequently been reported in studies with nintedanib.

Potential risks of nintedanib treatment also include arterial hypertension, GI perforations, thromboembolism and bleeding. Patients treated with full-dose anticoagulation or at known risk for bleeding were excluded from the INPULSIS trials. This has led to recommendations stating that patients at known risk for bleeding should be treated with nintedanib only if the anticipated benefit outweighs the potential risk. Although cardiac disorder AEs were balanced between the nintedanib and placebo groups, a higher proportion of patients in the nintedanib groups had myocardial infarctions. Conversely, a lower proportion of patients in the nintedanib groups had other ischemic heart disease. 'Other ischemic heart disease' was a pre-defined category including terms such as coronary artery disease, angina pectoris, coronary angioplasty, coronary artery stenosis, myocardial ischemia, coronary artery stent insertion, electrocardiogram (ECG) ST segment depression. The clinical significance of this finding is unknown, and further observation is needed.

For patients finalizing the 52 week study treatment in the TOMORROW and INPULSIS trials, participation in open label extension trials (1199.35 and 1199.33) was offered. Long term treatment in these still ongoing open label extension trials confirm the safety profile observed in the phase II and III trials [[P15-09876](#)].

Nintedanib has also demonstrated efficacy and tolerable safety in patients with non-small cell lung cancer who failed first line treatment [\[P11-00203\]](#), as well as in patients with advanced renal cell cancer [\[P13-06268\]](#), ovarian cancer [\[P11-10116\]](#) and hepatocellular carcinoma [\[P13-12693\]](#). Furthermore, nintedanib is also being investigated in other oncological indications, such as mesothelioma [\[P14-08020\]](#).

For a more detailed description of the drug profile, refer to the current Investigator's Brochure (IB) which is included in the Investigator Site File (ISF).

## 2. RATIONALE, OBJECTIVES, AND BENEFIT - RISK ASSESSMENT

### 2.1 RATIONALE FOR PERFORMING THE TRIAL

Until recently, IPF was essentially an untreatable disease. With the availability of specific antifibrotic drugs like nintedanib and pirfenidone, a major advance in the management of IPF has been achieved. However, based on the heterogeneity of disease progression and the lack of validated prognostic biomarkers, the clinical course in an individual patient remains unpredictable which is also true for the individual response to treatments.

Retrospective studies have identified several factors at a single point in time (baseline factors) or over time (longitudinal factors) that are associated with increased mortality in IPF. Change in physiologic measures over time, such as absolute decline in FVC % predicted normal by 10% or more, are associated with reduced survival; This association is only seen after a minimum of 6-12 months [[R06-4127](#); [R10-6539](#); [P05-02699](#); [R06-4126](#)]. However, change in pulmonary function in the prior year does not predict the subsequent change in pulmonary function in the following year [[R14-1149](#)]. In addition, none of these markers has been validated prospectively. Several serum proteins at baseline (e.g. KL-6, MMP-7, surfactant protein D) have also been shown to weakly correlate with the clinical course of the disease [[R15-4126](#) ; [R10-6378](#) ; [R15-4125](#)], but none of these markers have been assessed longitudinally.

A key hallmark in the pathology of IPF is dysregulation in connective tissue turnover within the lungs, resulting in excessive accumulation of distorted extracellular matrix and scarring which is considered a final common pathway in lung fibrosis. This deranged equilibrium is determined by several components including fibroblast proliferation, migration and differentiation, ECM synthesis by active myofibroblasts, collagen cross-linking and matrix degradation by various enzymes like metalloproteinases (MMPs).

The prospective observational PROFILE study [[R15-1220](#)] has recently shown that disease progression and prognosis can be determined through temporal changes in extracellular biomarkers indicating the defective and excessive matrix turnover potentially directly reflecting disease activity. In addition, the magnitude of change in ECM biomarkers related to the subsequent risk of disease progression and these changes provided the ability to predict outcome at an earlier stage (after 3 months) compared to physiologic measures of lung function. It remains to be determined whether baseline or change in ECM biomarkers will predict response to treatment.

Identifying biomarkers to predict the clinical course and benefits of nintedanib therapy, e.g. effect of nintedanib on surrogate biomarkers early in the course of the disease remains one of the most urgent and relevant challenges to improve overall patient management, prevent treatment delay or overtreatment.

This study is conducted to examine for the first time the treatment effect of nintedanib on change of biomarkers indicative of extracellular matrix turnover which have been shown recently to predict disease progression in the PROFILE study [[R15-1220](#)].

This study further aims to confirm the association of biomarker course during the first three months of treatment and disease progression as observed in PROFILE and to assess whether nintedanib treatment during the first 12 weeks alters this association or not.

## 2.2 TRIAL OBJECTIVES

The primary objective of the trial will be to assess the effect of nintedanib on rate of change in extracellular matrix (ECM) turnover biomarker CRPM over 12 weeks which has shown to strongly associate with disease progression in patients with IPF in the PROFILE cohort [\[R15-1220\]](#).

A secondary objective is to confirm the observed results from the PROFILE cohort, i.e. to assess the predictive value of change in extracellular matrix (ECM) biomarkers CRPM, C1M and C3M over 12 weeks for disease progression as defined by FVC decline  $\geq 10\%$  or death over 52 weeks [\[R15-1220\]](#). This will be done primarily within patients randomised to 12 weeks placebo treatment, since placebo treatment is expected not to impact change in extracellular matrix (ECM) biomarkers CRPM, C1M and C3M over 12 weeks nor disease progression which will facilitate interpretation of obtained results.

Additionally, a further secondary objective will be to assess how nintedanib treatment during the first 12 weeks of the trial affects the association between change in extracellular matrix (ECM) biomarkers CRPM, C1M and C3M over 12 weeks and disease progression. The corresponding analyses will comprise all patients treated with nintedanib including patients who are initially on placebo.

Analyses related to both primary and secondary objectives need to be considered as a whole in order to understand the complex network of associations between biomarkers, their change over time, the potential impact of treatment and the ultimate outcome of disease progression.

Further objectives are to assess the effect of nintedanib on rate of change in additional ECM turnover biomarkers and (based on the main and secondary objective) the predictive value of the corresponding rate of change for disease progression. Furthermore, the trial will evaluate changes in pulmonary function over time using home and standard in clinic spirometry and their correlation.

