### 3.2 DISCUSSION OF TRIAL DESIGN, INCLUDING THE CHOICE OF CONTROL GROUP(S)

Patients with idiopathic pulmonary fibrosis having a FVC of at least 80% of the predicted normal value at baseline will be eligible for participation in this trial. It is considered acceptable in this patient population to include a 12 week placebo-controlled treatment phase (refer to [Section 2.3](#)) in order to compare the effect of nintedanib versus placebo on change in ECM biomarker turnover.

In the PROFILE study [[R15-1220](#)], these biomarkers have shown their predictive potential for disease progression as early as after the period of 3 months.

A 1:2 randomisation (nintedanib:placebo) increases the number of patients treated with placebo during the first 12 weeks and consequently increases the power of assessing the association between change in the extracellular matrix (ECM) biomarker CRPM over 12 weeks and disease progression in placebo treated patients. Change in the extracellular matrix (ECM) biomarker CRPM over 12 weeks will be classified as stable or falling [ $\leq 0$  ng/ml/month] or rising [ $> 0$  ng/ml/month] in line with the PROFILE cohort [[R15-1220](#)].

Fibrotic remodelling of the lung interstitial tissue with subsequent restrictive ventilatory defect represents the core element of the histopathology of IPF. Therefore, FVC decline is considered a marker of disease progression and will be assessed via supervised spirometry at regular clinic visits as well as via home spirometry. Home spirometry may allow a more sensitive estimate of lung function decline based on more points of measurement resulting in higher accuracy and/or less variability in calculating the slope. Consequently, this study will also provide the opportunity to compare changes in FVC over the course of the study using standard clinic spirometry compared to home measurements, i.e. generate data on the general feasibility and validity of home spirometry in IPF.

After 12 weeks of double-blind treatment, all patients will enter the 40 week single active arm phase of the trial to potentially benefit from nintedanib treatment. Total treatment duration of 52 weeks is considered adequate to assess disease progression and the predictive value of ECM biomarker turnover in this patient population.

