Patient will need to perform at least one home spirometry manoeuvre between Visit 1 and Visit 2 (in order to obtain baseline PFT values) to be eligible for the trial.

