## **5. VARIABLES AND THEIR ASSESSMENT**

### **5.1 TRIAL ENDPOINTS**

Note that all endpoints based on spirometry are measured by clinic spirometry unless explicitly stated otherwise.

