### Measurements of in clinic FVC

Spirometry devices for in clinic measurements as well as devices for home spirometry will be supplied by a central vendor to all participating sites.

In clinic spirometry performance will be centrally reviewed. On-going feedback and training will be provided. Predicted normal values shall be calculated according to ECSC [\[R94-1408\]](#).

The spirometers and their use, including daily calibration, must meet ATS/ ERS criteria ([P05-12782](#)). Spirometry will be conducted while the patient is in a seated position. The test will be done in triplicate and selection of the best result done according to the guidelines. Spirometric results will be electronically transmitted and confirmed by central reading. Further details on in clinic spirometry shall be provided in the ISF.

For each patient, pulmonary function testing will always start at approximately the same time of the day within  $\pm 90$  minutes maximum difference from measurement time at Visit 1.

On days of clinic visits (including the screening visit), patients must refrain from strenuous activity at least 12 hours prior to pulmonary function testing.

Smoking should be discouraged throughout the study day (clinic visit) and will not be permitted in the 30-minute period prior to spirometry. Patients should also avoid cold temperatures, environmental smoke, dust, or areas with strong odours (e.g. perfumes).

Washout of bronchodilators (betamimetics and anticholinergics) need to be observed prior to in clinic spirometry (8 hours for short acting and 24 hours for long acting bronchodilators).

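### Correlation is the only home-versus-clinic measure named for change in FVC, and by itself it cannot support the validity aim or show which method gives the more precise slope

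*Protocol*

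**What the plan says.** Protocol Section 2.2 gives the home-spirometry objective in one sentence: "Furthermore, the trial will evaluate changes in pulmonary function over time using home and standard in clinic spirometry and their correlation". In the readable text of both documents, correlation is the only measure named for linking the two methods.

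Section 3.2 explains why home devices are used. They may help because more measurement points could be "resulting in higher accuracy and/or less variability in calculating the slope". The study therefore offers the chance to "compare changes in FVC over the course of the study using standard clinic spirometry compared to home measurements", and so to "generate data on the general feasibility and validity of home spirometry in IPF".

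Three other places matter:

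- Section 5.2 says of the clinic method: "In clinic spirometry performance will be centrally reviewed". A quality-controlled reference therefore exists.
- Section 3.3.3, in a footnote to the exclusion criteria, makes home data a condition of entry: "Patient will need to perform at least one home spirometry manoeuvre between Visit 1 and Visit 2".
- Section 5.1 says that "all endpoints based on spirometry are measured by clinic spirometry unless explicitly stated otherwise".

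The readable SAP describes no home-spirometry analysis. However, the synopsis list of further endpoints is blank, protocol numbering goes from 7.3.2 to 7.3.4, and the SAP goes from 5.2.2 to 6 and from 7.5.2 to 7.8. SAP Table 6.3:1 still lists further endpoints as analysed.

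**The concern.** Validity of one method against a reference asks whether the two give the same answer: how far apart they are on average, and how far apart they can be in one patient. Correlation asks only whether patients keep the same relative position under both. The measure named in Section 2.2 is therefore weaker than the aim in Section 3.2.

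Two readings would mislead. A high correlation could be taken as support for home spirometry although home decline is systematically too small or too large. A low correlation could be taken as evidence against it although the cause is noise, possibly in the clinic slopes. The possible gain in slope precision is a separate question, which a single correlation cannot answer because it is symmetric in the two methods.

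What is at stake is the interpretation of the home-spirometry data, not the trial's treatment comparison.

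**Working it through.** **Plan's own figure.** The documents give no sample size, precision or agreement limit for home versus clinic spirometry, so there is nothing to reproduce on this point. As a check of trial-level inputs only, protocol Section 7.7 states 88% power for 30% versus 50% in 233 placebo patients split equally (116.5 each): z = (0.20 − 1.96·√(2·0.24/116.5)) / √((0.21 + 0.25)/116.5) = (0.200 − 0.126)/0.0628 = 1.18, which is 88.1%. It reproduces and does not bear on what follows.

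**Step 1: offset and scale (algebra).** Write home change = a + b × clinic change + error, with b > 0. If s is the SD of clinic change and e the error SD, then r = b·s/√(b²s² + e²). The offset a does not appear, and with e = 0, r = 1 for every b > 0. To put sizes on this, assume a clinic change with mean −100 mL and SD 200 mL (not in the documents):

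| Home device | r | Mean difference, home − clinic (mL) | 95% limits of agreement (mL) | Concordance coefficient |
|---|---|---|---|---|
| Constant offset −150 mL | 1.00 | −150 | −150 to −150 | 0.78 |
| Records half the change | 1.00 | +50 | −146 to +246 | 0.76 |
| Records double the change | 1.00 | −100 | −492 to +292 | 0.76 |
| Unbiased, error SD 100 mL | 0.89 | 0 | −196 to +196 | 0.89 |
| Unbiased, error SD 200 mL | 0.71 | 0 | −392 to +392 | 0.67 |
| Unbiased, error SD 400 mL | 0.45 | 0 | −784 to +784 | 0.33 |

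For the half-scale row, the mean difference is −50 − (−100) = +50, the SD of the differences is 0.5 × 200 = 100, and the limits are 50 ± 196. The three biased devices have perfect correlation; the three unbiased ones do not.

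**Step 2: ceiling from clinic noise.** For an error-free home device, the correlation of slopes cannot exceed √(σ²/(σ² + ε²/Sxx)). Here σ is the SD of true slopes, ε the clinic reading error, and Sxx the sum of squared deviations of the visit times. Protocol Section 6.1 gives clinic visits at weeks 0, 4, 8, 12, 16, 20, 24, 36 and 52. For all nine, Sxx = 2169 wk² = 2169/52² = 0.802 yr². For weeks 0 to 12 it is 80 wk² = 0.0296 yr². Assumed: σ 150–350 mL/yr and ε 80–160 mL, with middle case 250 and 120.

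- 52 weeks, middle case: ε²/Sxx = 14,400/0.802 = 17,953; √(62,500/80,453) = 0.88. Range 0.64–0.97.
- 12 weeks, middle case: 14,400/0.0296 ≈ 486,700; √(62,500/549,200) = 0.34. Range 0.16–0.60.

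**Step 3: agreement on the same data.** Take the 52-week middle case and further assume weekly home readings (weeks 0 to 52, Sxx = 12,402 wk² = 4.59 yr²), home error SD 200 mL and mean decline 200 mL/yr. The home slope error variance is 40,000/4.59 ≈ 8,721.

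- Correct device: r = 62,500/√(80,453 × 71,221) = 0.83.
- Half the decline and half the noise: r is again 0.83, while decline is understated by 100 mL/yr.
- Half the decline, same noise: r = 31,250/√(80,453 × 24,346) = 0.71, with the same 100 mL/yr understatement.

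The paired mean difference at n = 350 has standard error √((17,953 + 8,721)/350) = 8.7 mL/yr for the correct device and 10–11 mL/yr for the half-scale devices. A 100 mL/yr bias would be plain.

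**Step 4: precision needs no extra patients.** With one pair per patient and 350 evaluable, the 95% CI half-width is 1.96/√350 = 0.10 SD of the differences for the mean and 1.96·√(1/350 + 1.96²/(2·349)) = 0.18 SD for each limit. With 250 evaluable these become 0.12 and 0.21 SD.

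**The case against.** The strongest reply is that the analysis itself cannot be seen. The sections that would define and analyse further endpoints are not public, and an objectives sentence is not an analysis specification. A reader might infer that the plan omits an agreement analysis; the documents do not support that, and text withheld from publication cannot be counted as missing. This part stands, and it makes the recommendation conditional.

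Next, a reader might infer that correlation is the whole answer to the objective. Section 2.2 names two things, the changes by each method and their correlation, and Section 3.2 speaks of comparing changes. Mean changes reported side by side in the same patients would reveal an average bias. This also stands. What side-by-side means do not supply is a paired interval for the difference, the spread of disagreement within patients, or slope precision by method.

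A reader might also infer that the protocol promises to show accuracy. It does not: "Home spirometry may allow a more sensitive estimate of lung function decline based on more points of measurement resulting in higher accuracy" is conditional, and for validity it undertakes only to produce data.

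Finally, the numbers depend on assumptions. A half-scale device matches the correct one on r only if its noise shrinks too; otherwise r falls from 0.83 to 0.71, so correlation does respond. No readable text ties the correlation to 12 weeks or sets a threshold for calling home spirometry valid, so the low 12-week ceilings only show how the ceiling depends on follow-up. These limits are accepted. They do not affect the algebra in step 1.

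**Conclusion.** The point holds in a narrow form. The one measure named for linking home and clinic change cannot by itself support the validity aim of Section 3.2, or show which method gives the more precise slope. That conclusion rests on the definition of correlation and needs no assumed value.

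Its size is modest. It touches a further objective; the primary endpoint is a blood biomarker, and the key secondary endpoint uses supervised clinic spirometry. No treatment comparison in the readable text depends on home–clinic agreement. The correlations and mL/yr values above rest on assumed slope variation, reading errors, mean decline and home reading frequency, none of which the documents give. Whether the unpublished sections already deal with this cannot be judged. It is best treated as a nearly free improvement.

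**What to change.** In Section 2.2 and in the home-spirometry analysis, unless already specified there:

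- Make agreement the validity measure. Report the paired mean difference in FVC slope (home minus clinic) over 52 weeks with its 95% CI, and Bland-Altman 95% limits of agreement. When interpreting the limits, note that they include clinic as well as home error.
- For the suggested gain in precision, compare the within-patient residual SD and the standard error of the slope between the two methods.
- Keep the correlation as a descriptive figure.

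Cost: one sentence in the protocol objective and the SAP, plus one table and one plot. It needs no further patients, visits or measurements.
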